12.7. Analyses of Safety

All safety summaries will be descriptive; no statistical testing will be performed.

12.7.1. Adverse Events

A TEAE is defined as an adverse event with an onset that occurs after receiving study drug, or a continuing adverse event diagnosed prior to the date of first dose of study drug that increases in severity after the start of dosing. Adverse events will be categorized by system organ class and preferred term with the Medical Dictionary for Regulatory Activities (MedDRA).

Summary tables for TEAEs will include number and percent of subjects experiencing TEAEs by system organ class and preferred term. If a subject has more than one TEAE that codes to the same preferred term, the subject will be counted only once for that preferred term. Similarly, if a subject has more than one TEAE within a system organ class category, the subject will be counted only once in that system organ class category.

The following TEAE summaries will be provided for the Treatment Period:

- Overall summary of TEAEs
- TEAEs by system organ class and preferred term
- Drug-related TEAEs by system organ class and preferred term
- TEAEs by system organ class, preferred term, and severity
- Serious TEAEs by system organ class and preferred term
- TEAEs leading to study drug discontinuation by system organ class and preferred term

12.7.2. Clinical Laboratory Tests

Mean changes from baseline will be summarized descriptively for each clinical laboratory parameter.

Clinical laboratory results considered clinically important by the Investigator will be identified. Individual results for clinical laboratory tests (serum chemistry, hematology, and urinalysis) outside the normal range will be flagged in the data listings.

Clinical laboratory assessments will be conducted by a central laboratory.

12.7.3. Electrocardiogram

The interpretation of ECG and interval duration measurements by the designated ECG laboratory cardiologists will be reviewed by the Investigator. Clinically significant deteriorations from baseline will be reported and summarized as TEAEs.

12.7.4. Vital Sign Measurements

Mean change from baseline will be summarized descriptively for each vital sign.

12.7.5. Suicidal Ideation

Subjects with suicidal ideation or behavior will be identified with the S-STS.

12.8. Interim Analysis

No interim analysis is planned for this study.

13. ADMINISTRATIVE

13.1. Source Documents

Source documents are defined as the result of original observations and activities of a clinical investigation. Source documents may include, but are not limited to, study progress notes, e-mail correspondences, informed consent forms, clinical laboratory reports, medical histories, hospital records, and drug accountability records. All source documents will be maintained by the Investigator(s) and made available for inspection by Sponsor representatives, the FDA, and other applicable regulatory authorities.

13.2. Study Monitoring

Site visits will be conducted by an authorized Sponsor representative (Site Monitor) to inspect study data, source documents, and eCRFs in accordance with International Council for Harmonisation (ICH) guidelines, Good Clinical Practice (GCP), and local regulations or guidelines. The Monitor will inspect the study data at regular intervals throughout the study to verify adherence to the protocol, as well as completeness, consistency, and accuracy of study data.

Aptinyx is also collecting the impact of COVID-19 on visits (e.g. incomplete or remote visits, dosing interruptions, changes in planned IP dispensation).

The Investigator will permit Sponsor representatives, its third-party vendors, the FDA, and/or respective health authorities to inspect facilities and records relevant to this study.

13.3. Case Report Forms

An eCRF will be used to record all subject data required in this protocol. The eCRF must be completed by designated and trained study personnel. The eCRF will be signed by the Principal Investigator or a Subinvestigator listed on the FDA Form 1572. It is the responsibility of the Principal Investigator to ensure the eCRFs are completed and submitted to Aptinyx (or designee) in an accurate and timely manner. The processing of eCRFs will include an audit trail (to include changes made, reason for change, date of change, and person making the change).

13.4. Protocol Amendment(s)

If a protocol has been filed with regulatory agencies or submitted to an IRB and requires changes, a protocol amendment must be written. The Sponsor will make changes to the protocol. All amendments will be sent to a central IRB on the study sites' behalf, if applicable. Sites using a local IRB are responsible for submitting the amendment for review and approval.

13.5. Audits and Inspections

During the course of the study or after completion of the study, each study site may be subject to an audit by an Aptinyx Quality Assurance Auditor (or an auditor appointed by Aptinyx or its authorized representative) and/or an inspector from the FDA and/or other regulatory authority. Every attempt will be made to notify the Investigator in writing in advance of the audit.

13.6. Institutional Review Board

This protocol, the informed consent document, and all relevant supporting data must be submitted to the IRB for approval. Institutional Review Board approval of the protocol, informed consent documents, any subject-facing materials, and any advertisement used to recruit study subjects must be obtained before the study may be initiated. The IRB must comply with requirements set forth in the Code of Federal Regulations (CFR) part 56.

The Investigator is responsible for keeping the IRB advised of the progress of the study, changes to research activity, unanticipated problems involving risk to human subjects or others and any changes made to the protocol, as deemed appropriate, but in any case, at least once a year. The Investigator is also responsible for notifying the IRB of any significant adverse events or protocol deviations that occur during the study and meet IRB reporting requirements.

The Investigator agrees that he/she will not make any changes in the research without IRB approval, except where necessary to eliminate apparent immediate hazards to human subjects, as referenced in 21 CFR 312.66.

13.7. Compliance with Regulatory Requirements

This study will be conducted in compliance with the protocol and all regulatory requirements, in accordance with GCP, including ICH Guidelines, and in general conformity with the most recent version of the Declaration of Helsinki.

13.8. Informed Consent

Written informed consent must be obtained from potential study subjects prior to the initiation of any study-related procedures. This study may employ electronic informed consent. Electronic or digital signatures (compliant with 21 CFR § 11 regulations for collecting and storing digital signatures) may be captured indicating the patient's willingness to participate in the clinical trial. The use of electronic informed consent supplements the interaction between the participant and the research staff, and it provides an opportunity for remote conduct of study activities in the setting of the COVID-19 Health Emergency. The informed consent document may be executed up to 30 days prior to the screening visit. The date the first screening related activity is completed will be considered the subject's screening date. If the subject does not complete the screening visit within 30 days of signing the informed consent document, the subject must be reconsented. The original signed informed consent form for each participating subject shall be filed with records kept by the Investigator(s). A copy of the signed informed consent document must be provided to the subject. If applicable, written consent will be obtained using a certified translation. If the informed consent form is revised, subjects actively participating in the study must be reconsented in a timely manner.

13.9. Study File Management

The Investigator is responsible for ensuring that the study files are maintained. The study file will include, but is not limited to, source documents, correspondence, regulatory documents (IRB approvals/correspondence, study logs, FDA 1572 forms, financial disclosures, clinical study material records, study drug accountability records, and medical records).

13.10. Study Completion

Aptinyx requires the following data and materials be completed before a study can be considered terminated or completed: source documents are completed, study drug reconciliation activities are completed, and study procedures and assessments are source verified and completed.

13.11. Confidentiality

Personal study subject data collected and processed for the purposes of this study should be managed by the Investigator and his/her staff with adequate precautions to ensure the confidentiality of personal health information, and in accordance with applicable national and/or local laws and regulations on personal health information protection.

Monitors, auditors, and other authorized agents of Aptinyx, the IRB approving this research and applicable regulatory authorities will be granted direct access to the study subjects' original medical records for verification of clinical study procedures and/or data, without violating the confidentiality of the subjects, to the extent permitted by the law and regulations. In any presentation of the results of this study at meetings or in publications, the subjects' identities will remain confidential.

13.12. Compensation, Insurance, and Indemnity

Information regarding compensation, insurance, and indemnity is addressed in the Clinical Trial Research Agreement.

13.13. Financial Disclosure

The Investigator(s) are responsible for providing financial disclosure(s) in covered clinical studies. Principal Investigators and Subinvestigators are required to disclose applicable financial information, and to promptly update Aptinyx with any relevant changes throughout the study and for one (1) year after study completion.

13.14. Records Retention

According to United States Investigational New Drug regulations (21 CFR 312.62), records and documents pertaining to the conduct of this study and the distribution of study drug including but not limited to source documents, eCRFs, informed consent forms, clinical laboratory test results, and drug inventory records will be retained. These records will be kept on file by the Principal Investigator for two years after a marketing application is approved for the drug for the indication for which it is being studied. If no application is filed or approved, these records must be kept for two years after the investigation has been discontinued and the FDA has been notified. Per ICH guidelines, documents should be retained until at least two years after the last approval of a marketing application in an ICH region and until there are no pending or

contemplated marketing applications in an ICH region, or at least two years have elapsed since the formal discontinuation of clinical development of the study drug. Aptinyx will notify the Investigator when records and documents no longer need to be retained. No study records should be destroyed without prior authorization.

13.15. Publication Policy

The publication policy is outlined in the Clinical Trial Agreement.

15. APPENDICES

15.1. Disallowed Analgesic and Other Medications*

Washout of the following disallowed analgesics should be completed during screening, with the last dose being at least 2 weeks prior to randomization.

- Tricyclic antidepressants (TCAs)
- Norepinephrine reuptake inhibitors (NRIs), e.g., atomoxetine (Strattera[®]) and bupropion (Wellbutrin[®], Zyban[®])
- Serotonin-norepinephrine reuptake inhibitors (SNRIs), e.g., milnacipran (Savella), duloxetine (Cymbalta[®]), venlafaxine (Effexor[®]), Desvenlafaxine (Pristiq[®]), levomilnacipran (Fetzima[®])
- Anti-epileptics, e.g., gabapentin (Neurontin[®]) and pregabalin (Lyrica[®]); NMDA receptor ligands
- Opioids
- NSAIDs (except as described in section 8.7)
- Benzodiazepines except alprazolam or lorazepam
- Muscle relaxants
- Acetaminophen or acetaminophen containing therapies for indications other than fibromyalgia
- Topical therapies: topical capsaicin; topical/local anesthetic lidocaine

*Any non-pharmacologic therapies or interventions for treatment of pain that are not on this list needs to be discussed with the Medical Monitor prior to screening (e.g., nerve blocks, spinal stimulators, etc.).

Subjects must be stable for at least seven (7) days prior to randomization. The “stable” condition is based on investigators’ clinical judgment. It means no significant withdrawal effects, and to be stable regarding their pain, i.e., subjects should not be in a flare state with much worse pain than before washout as is common with discontinuation of any drugs but most common with NSAIDs and opioids.

Prohibited medications must not be withdrawn for participation in this study when prescribed for a condition other than pain.

1 INTRODUCTION

This document details the planned statistical analyses for the Aptinyx Inc, protocol NYX-2925-2005 study titled “A Randomized, Double-Blind, Placebo-Controlled Study to Assess the Efficacy and Safety of NYX-2925 in Subjects with Fibromyalgia”.

The proposed analyses are based on Protocol Version 7.0 Amendment 6, dated [REDACTED].

This is a 13- to 16-week study that includes a 1- to 4-week Screening Period followed by a 12-week, double-blind, randomized, placebo-controlled Treatment Period in which subjects will take one capsule of study drug once daily by mouth for up to 12 weeks.

Rescue medication, which consists of 500 mg tablets of acetaminophen, is also provided by sponsor. Subjects will be instructed to take one to two 500 mg tablets every 6 hours as needed up to 6 tablets total for pain associated with fibromyalgia, not to exceed 3 g/day. A safety follow-up call is also to be made to the subjects within 10 days and then approximately 30 days after week 12 final visit to assess for any adverse event/serious adverse event (AE/SAE) closure and any newly reported SAEs.

2 STUDY OBJECTIVES

2.1 Primary Objectives

The primary objectives of this study are:

- To evaluate the efficacy of NYX-2925 taken orally once daily versus placebo for the treatment of fibromyalgia.
- To assess safety and tolerability of NYX-2925 taken orally once daily.

2.2 Secondary Objectives

The secondary objective of the study is:

- To assess effects of NYX-2925 taken orally once daily versus placebo on general pain, sleep interference, fatigue, physical functioning, psychological state and global improvement.

3 ENDPOINTS

3.1 Primary Endpoint

The primary efficacy endpoint is the change from baseline to Week 12 in the weekly mean of the daily Numerical Rating Scale (NRS) score assessing average pain intensity related to fibromyalgia in the past 24 hours.

3.2 Secondary Endpoints

The secondary efficacy endpoints are:

- Percentage of subjects “much improved” or “very much improved” on the Patient Global Impression of Change (PGI-C) at Week 12.
- Change from baseline in the weekly mean of the Daily Sleep Interference Scale (DSIS) scores at Week 12.
- Percentage of subject achieving $\geq 30\%$ pain reduction from baseline in the weekly mean NRS average pain intensity at Week 12.
- Percentage of subjects achieving $\geq 50\%$ reduction from baseline in the weekly mean NRS average pain intensity related to fibromyalgia at Week 12.
- Change from baseline to Week 12 in the Fibromyalgia Impact Questionnaire - Revised (FIQR) score.
- Change from baseline to Week 12 in the Patient Reported Outcome Measurement Information System – Fibromyalgia (PROMIS_{FM}) sleep disturbance score.
- Change from baseline to Week 12 in the Patient Reported Outcomes Measurement Information System - (PROMIS) fatigue profile score.
- Change from baseline to Week 12 in the Patient Reported Outcomes Measurement Information System (PROMIS) physical function score.
- Cumulative response (percent reduction from baseline) in the weekly mean NRS average pain intensity at Week 12.
- Use of rescue medication, including the proportion of subjects using rescue medication, the frequency and amount used.
- Change from baseline in the weekly mean of the daily Numerical Rating Scale (NRS) at each week from Week 1 through Week 12.

3.3 Other Efficacy Endpoints

3.4 Safety Endpoints

The safety endpoints will include adverse events (AE), serious adverse events (SAE), discontinuation due to adverse events and the S-STS. Vital signs, physical examination, electrocardiogram and standard clinical laboratory parameters will also be assessed.

4 SAMPLE SIZE

The planned sample size is a total of 300 randomized subjects with 100 subjects per treatment group. Efficacy analyses will include all subjects who receive at least one dose of study drug and who have at least one post baseline assessment. It is expected that approximately 15% of subjects will be excluded from the efficacy population. A total of 85 subjects per treatment arm will provide approximately 88% power to detect a difference in means of 0.73 for NYX-2925 50 mg or 100 mg versus Placebo group assuming that the common standard deviation is 1.7 without correcting for multiple testing, using one-sided statistical testing with an overall Type I error rate of 0.05.

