12.6.4. Other Efficacy Analyses

12.6.5. Multiple Comparisons

The primary efficacy endpoint and primary statistical analysis are protocol specified.

The primary efficacy endpoint and other selected efficacy endpoints will be tested (using MMRM as described above) to preserve the overall Type I error rate.

There will be no other adjustments for multiple comparisons.

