6.11 Efficacy Analyses

All statistical tests will be performed using a one-tailed 5% overall significance level as primary analysis. All comparisons between treatments will be reported with one-sided 95% confidence intervals (CI). All analyses will be performed independently on the treatment groups.

All statistical tests will be repeated using a two-sided 5% overall significance level, unless otherwise stated. All comparisons between treatments will be also reported with two-sided 95% CI.

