6.11.1 Primary Endpoint

The primary efficacy endpoint is the change from baseline to Week 12 in the weekly mean of the daily NRS score assessing average pain intensity in the past 24 hours. The hypothesis for one-sided testing between NYX-2925 50mg- and placebo- treated groups is as follows:

$$H_0 = \mu_{NYX,50\ mg} - \mu_{placebo} \geq 0 \quad \text{versus} \quad H_1 = \mu_{NYX,50\ mg} - \mu_{placebo} < 0$$

The hypothesis for testing between NYX-2925 100 mg- and placebo- treated groups is as follows:

$$H_0 = \mu_{NYX,100\ mg} - \mu_{placebo} \geq 0 \quad \text{versus} \quad H_1 = \mu_{NYX,100\ mg} - \mu_{placebo} < 0$$

Where $\mu_{NYX,50\ mg}$ denotes the mean change from baseline to Week 12 in the weekly mean of the NRS score in the NYX-2925 50 mg treatment group, $\mu_{NYX,100\ mg}$ denotes the mean change from baseline to Week 12 in the weekly mean of the NRS score in the NYX-2925 100 mg treatment group and $\mu_{NYX,placebo}$ denotes the mean change from baseline to Week 12 in the weekly mean of the NRS score in the placebo group.

The hypothesis for two-sided testing between NYX-2925 50mg- and placebo- treated groups is as follows:

$$H_0 = \mu_{NYX,50\ mg} - \mu_{placebo} = 0 \quad \text{versus} \quad H_1 = \mu_{NYX,50\ mg} - \mu_{placebo} \neq 0$$

The hypothesis for testing between NYX-2925 100 mg- and placebo- treated groups is as follows:

$$H_0 = \mu_{NYX,100\ mg} - \mu_{placebo} = 0 \quad \text{versus} \quad H_1 = \mu_{NYX,100\ mg} - \mu_{placebo} \neq 0$$

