6.11.2 Primary Efficacy Analysis

A one-tailed restricted maximum likelihood (REML)-based mixed model for repeated measures (MMRM) with one sided 95% CI will be utilized to assess the difference between treatment groups with respect to change from baseline to Week 12 in the weekly mean of the NRS score assessing average pain intensity in the past 24 hours.

The MMRM model will have site, treatment group, week, baseline NRS score, and treatment-by-week interaction as terms in the model. The unstructured covariance (UN) will be utilized as the within-subject covariance structure. In the event that the model fails to converge using the UN, the

Fisher scoring algorithm (via the SCORING option of the PROC MIXED statement) will be used to obtain the initial values of covariance parameters, otherwise, no-diagonal factor analytic structure (via the TYPE = FA0(T) option of the REPEATED statement) will be used as another option. When the above strategy fails, the successive univariate regression method will be applied. The Kenward-Roger degrees of freedom correction will also be used for this analysis.

The estimate of the difference between NYX-2925 50 mg versus placebo and NYX-2925 100 mg versus placebo at Week 12 and standard error (SE) will be derived from this model. Observed NRS scores at baseline and at each week, as well as their change from baseline at each week will be presented by treatment groups. The LS means, corresponding SEs, and 95% CI for each treatment group, the treatment difference of LS means, corresponding SEs, 1-sided 95% CI and 1-sided p-value at each week will be presented. The upper limit of the 95% CI of treatment difference will be extracted using ALPHA=0.10 statement for the bound in the unfavorable direction, and the limit in the favorable direction will be set to negative infinity.

The following is the sample SAS code that will be used for this analysis:

```
PROC MIXED DATA= DATAIN;
  CLASS USUBJID TREATMENT WEEK SITE;
  MODEL CHG = TREATMENT WEEK SITE TREATMENT*WEEK BASELINE / DDFM=KR;
  REPEATED WEEK / SUBJECT=USUBJID TYPE=UN;
  * extract two-sided 95%CI of LS MEANS each treatment groups by week;
  LSMEANS TREATMENT*WEEK / DIFF CL;
  * extract one-sided 95%CI of LS MEANS each treatment groups by week;
  LSMEANS TREATMENT*WEEK / DIFF CL ALPHA=0.10;
  RUN;
```

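### SAP 4 and 6.11 call one-sided 5% an overall error rate, but it applies to each dose separately; across the two unadjusted dose tests the false-positive risk is about 8.8%

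*SAP*

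**What the plan says.** SAP 4 assumes 85 evaluable subjects per arm, a difference of 0.73 and an SD of 1.7. It gives about 88% power for either dose against placebo, "without correcting for multiple testing, using one-sided statistical testing with an overall Type I error rate of 0.05".

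SAP 6.11 repeats the label: "All statistical tests will be performed using a one-tailed 5% overall significance level as primary analysis". It adds "All analyses will be performed independently on the treatment groups", and then applies the same word to the second set of tests: "All statistical tests will be repeated using a two-sided 5% overall significance level, unless otherwise stated".

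SAP 6.11.1 writes a null hypothesis for 50 mg and then a separate one, introduced by "The hypothesis for testing between NYX-2925 100 mg- and placebo- treated groups is as follows". SAP 6.11.2 derives "The estimate of the difference between NYX-2925 50 mg versus placebo and NYX-2925 100 mg versus placebo at Week 12" from the MMRM. Its sample code takes the one-sided bound from "LSMEANS TREATMENT*WEEK / DIFF CL ALPHA=0.10", which is one-sided 5% for each contrast.

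SAP 6.11.6, the multiplicity section, declines adjustment for secondary and other endpoints and is silent on the two primary dose comparisons. Addendum 2.3.2, written after unblinding, restates the one-tailed model and adds no procedure.

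Protocol 12.6.5 says: "The primary efficacy endpoint and other selected efficacy endpoints will be tested (using MMRM as described above) to preserve the overall Type I error rate". It names no method and rules out any further adjustment. Protocol 12.1 puts the overall rate at 0.05, with power of about 80%.

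**The concern.** An overall Type I error rate is normally read as the chance of any false positive in the family of tests that supports the claim. SAP 4 says in one sentence that nothing is corrected and that the rate is overall. With two tests at the full 5%, both statements cannot be true in that sense.

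At stake is the error rate attached to the primary efficacy claim. Neither document defines a positive trial, so treating significance on at least one dose as the decision event is my reading. The documents lean that way: SAP 6.11.3.2 starts the tipping-point analysis if the primary result favours any active group, and Protocol 12.6.2 does so for one or both doses. A reader who relies on Protocol 12.6.5 would expect 5% to cover both doses.

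**Working it through.** **Inputs.** From SAP 4: 85 evaluable per arm (100 randomised per arm, 15% excluded), difference 0.73, SD 1.7, one-sided alpha 0.05. From SAP 6.11.1 and 6.11.2: two contrasts, 50 mg and 100 mg, each against the same placebo arm.

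**Step 1: reproduce the stated power.** The noncentrality is difference / (SD × √(2/n)) = 0.73 / (1.7 × √(2/85)) = 2.799.

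| Alpha per dose (one-sided) | Power, normal: Φ(2.799 − z) | Power, noncentral t (168 df) |
|---|---|---|
| 0.05 (z = 1.645) | 87.6% | 87.4% |
| 0.025 (z = 1.960) | 79.9% | 79.5% |

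The stated 88% is recovered when each dose receives the full 5%, and not when 5% is split between the doses. The 0.05 in SAP 4 is therefore a per-comparison rate.

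**Step 2: correlation of the two contrasts.** Through the shared placebo arm, correlation = √(n1·n2 / ((n1+n0)(n2+n0))). With 85 in every arm this is 85/170 = 0.500.

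**Step 3: error across the two doses when neither works.** P(at least one favourable rejection) = 2 × alpha − P(both reject), with P(both) from a bivariate normal. At one-sided 0.05 and correlation 0.5 this is 0.10 − 0.0122 = 0.0878. Two simulations using a pooled t with 252 df gave 0.0875 and 0.0879. Independent tests would give 1 − 0.95² = 0.0975, and the upper bound is 0.10.

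**Step 4: sensitivity to arm sizes.** The documents give no final arm sizes, so 75 to 95 per arm is an assumption.

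| Active / active / placebo | Correlation | Each dose at 0.05 | Each dose at 0.025 |
|---|---|---|---|
| 95 / 95 / 75 | 95/170 = 0.559 | 8.6% | 4.5% (0.0445) |
| 85 / 85 / 85 | 0.500 | 8.8% | 4.5% (0.0454) |
| 75 / 75 / 95 | 75/170 = 0.441 | 9.0% | 4.6% |

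Over correlations from 0.4 to 0.6, the figure at one-sided 0.05 runs from 9.1% down to 8.4%.

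**Step 5: the repeated two-sided tests.** Two-sided 5% per dose at correlation 0.5 gives 9.1% counting either direction and 4.5% in the favourable direction. The label is therefore also wrong for these tests if both directions count.

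**For scale.** A true one-sided 5% across both doses would have meant power per dose of about 79.9% with Bonferroni (0.025 each) or 81.1% with Dunnett (about 0.0277 each), against 87.6%.

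**The case against.** The strongest reply is that the substance is already disclosed. SAP 4 says there is no correction, SAP 6.11 says the treatment groups are analysed independently, and each dose has its own hypothesis. A careful reader will see that 5% applies to each dose. In SAP 6.11 the label covers every test, including unadjusted secondary ones, so it may only be loose wording. All of this stands and limits the harm, but it does not make the label right.

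Second, the protocol may have used the word in the same way. If its testing was two-sided and the SAP 4 inputs applied, unadjusted two-sided 5% per dose gives 79.9%, matching the protocol's figure of about 80%. Control across both doses at two-sided 5% (one-sided 0.0125 each) would give only about 71%. This is suggestive and no more: one-sided 0.025 per dose also gives 79.9%, and the protocol states no effect size or SD. Protocol 12.6.5 also speaks of endpoints and never of doses. Even so, it says the primary endpoint is tested so as to preserve the overall rate, and that endpoint is tested twice.

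Third, this is a phase 2 study, and 100 mg was added to learn about dose response. If each dose is judged strictly on its own, 5% per dose is the relevant rate. That is a fair position, but then the plan should call the rate per-comparison.

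Finally, the SAS code is only a sample, so a missing adjustment option proves little alone. The conclusion rests mainly on the power figure, the separate hypotheses and the silence of SAP 6.11.6.

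**Conclusion.** The concern holds. The 5% in SAP 4 and 6.11 is a per-comparison rate labelled as overall, at odds with Protocol 12.6.5. If neither dose works, the chance of at least one favourable false positive is about 8.8%, or 8.6% to 9.0% for the assumed unequal arms. This rests on both nulls being true, one-sided 5% on each dose, a shared placebo arm, and a finding on either dose counting as success. The 88% stands as per-dose, uncorrected power.

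One bullet in SAP 9 is blacked out and might record the change; the readable bullets record only the move from two-sided to one-sided testing. The point should be fixed because it misstates the error rate of the primary claim, but no analysis, estimate or power figure has to be recalculated.

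**What to change.** The addendum records that the study is already unblinded, so disclose and do not set a new success threshold. In a further addendum and in the study report:

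1. Replace the word overall with per-comparison in SAP 4 and in both places in SAP 6.11, and state in SAP 6.11.6 that the two primary dose comparisons are not adjusted.
2. State the family-wise error of about 8.8% if neither dose works. List the departure from Protocol 12.6.5 in SAP 9, unless the blacked-out bullet already does so.
3. Describe the 88% as per-dose, uncorrected power, with about 80% at one-sided 0.025 per dose alongside it.
4. Report for each dose whether it also meets one-sided 0.025, that is, two-sided p<0.05 with the estimate favouring NYX-2925. Planned Table 14.2.1.1.2 supplies this. The favourable-direction error across both doses at that level is about 4.5%. Present it as disclosure and not as a success rule.

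The cost is wording in SAP 4, 6.11, 6.11.6 and 9 and in the study report, with no new data or tables. The sponsor would have to state about 8.8% where the plan now says 5%. After unblinding, error control can be described accurately but not restored.
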